1. Risks Associated with Standardized Assessments: The standardized assessments administered during baseline and monthly research interviews will include: (1) demographic information, including age, race, and gender; (2) health care status, including past medical history, current medications, (3) standardized screening for mental illness using the Center for Epidemiologic Studies Depression Scale (CES-D);¹²¹ (4) standardized measures of drug use, including determination of DSM-V criteria for cocaine use disorder;¹²² (5) Addiction Severity Index (ASI)-Lite to assess cocaine use, polysubstance use and severity;^{123,124} (6) LifeWindows questionnaire to measure the Information-Motivation-Behavioral constructs of adherence;^{111,125} (7) ART adherence using blister pack, Visual Analog Scale (VAS) and brief adherence scale;^{126,127} (8) change in cocaine use using the Timeline Follow-Back (TLFB);¹²⁸ (9) AUDIT-C to assess alcohol use;¹²⁹ (10) health literacy;¹³⁰ (11) social support;¹³¹ (12) trust in physicians;¹³² (13) acceptance of smart pill box and smartphones;¹³³ and (14) perceived source credibility¹³⁴, (15) neighborhood delineation using the Activity Space; and (16) mapping and interpreting social or personal networks using a egocentric social network analysis questionnaire. It is possible that participants may feel uncomfortable answering these questions; in this case, they will be able to refuse answering any questions that they do not wish to answer.

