Aim 2 (Pilot Feasibility Study): The primary outcomes will be ART adherence and persistence, measured as a composite score ranging from 0 to 100%, and as number of continuous days taking ART without a 7-day (or 3-day) gap^{18,71} respectively. Outcome analyses will be conducted for (a) adherence and persistence behavior, (b) drug outcomes (cocaine use), (c) HIV treatment outcomes (VL<20 copies/mL; change in CD4+ T lymphocytes), and (d) ART-related Information, Motivation, and Behavioral Skills constructs. The general framework for discerning differences between study conditions on main outcome variables will be to perform 3 (intervention condition) x 3 (repeated follow-up assessments) mixed design analysis entering pre-intervention scores as covariates and additional theoretically and empirically relevant covariates (such as baseline mental status etc.). For variables that are approximately normally distributed, we will use multivariate analyses of covariance (MANCOVA), with significant multivariate tests followed by subsequent analyses of co-variance (ANCOVA). Variables that violate distributional assumptions of normality will be analyzed using generalized linear model (GLM) procedures, which enable the use of non-Gaussian error models. Based on a review of the literature, GLM is the most appropriate approach for variables with strong positive skew, e.g., adherence.

[figure not shown]
To examine the mediating and moderating effects of activity space and social network facilitators and barriers on primary (ART adherence and persistence) and secondary outcomes (HIV viral suppression, cocaine use, retention in HIV care), the following steps are going to be followed:

- a. A range of variables associated to activity space and social networks (both risk and support) will be calculated using a combination of GIS, SNA, and spatial statistics methods. The variables will be the covariates.
- b. The outcome variables are: primary (ART adherence and persistence) and secondary outcomes (HIV viral suppression, cocaine use, retention in HIV care).
- c. We will first use descriptive statistics, bivariate correlation, and t-tests to understand the distribution and association of all the covariates calculated in step#a with the outcome variables (step#b).
- d. After running tests of multicollinearity, only uncorrelated covariates at $p \leq 0.05$ (considered statistically significant) will be included in the subsequent mediation and moderation analysis.

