- e. Using the framework of structural equation modeling, we will identify the moderating and/or mediating effects of spatial (activity space and neighborhood levels) and non-spatial data (individual and interpersonal) covariates on the primary and secondary outcomes.

A comparative analysis will be conducted to contrast the model performance (R², AIC, and RMSE) of two mediation/moderation models with the primary (ART adherence) and a secondary (HIV viral suppression) outcome: 1) with social network metrics and b) with spatial-social network metrics (calculated in step#a).

SECTION VII: RECRUITMENT/CONSENT AND ASSENT PROCEDURES

1. Targeted Enrollment: Give the number of subjects:

a. targeted for enrollment at Yale for this protocol ____

Aim 1 (Focus Groups): 42 (30 PLH cocaine users; 12 healthcare providers)

Aim 2 (Pilot Feasibility Study): 90 PLH with co-occurring CUD

b. If this is a multi-site study, give the total number of subjects targeted across all sites ____

2. Indicate recruitment methods below. Attach copies of any recruitment materials that will be used.

- | | | |
|--|---|-------------------------------------|
|  Flyers |  Internet/Web Postings |  Radio |
|  Posters |  Mass E-mail Solicitation |  Telephone |
|  Letter |  Departmental/Center Website |  Television |
|  Medical Record Review |  Departmental/Center Research Boards |  Newspaper |
|  Departmental/Center Newsletters |  Web-Based Clinical Trial Registries | |
|  YCCI Recruitment database |  Clinicaltrials.gov Registry (do not send materials to HIC) | |
|  Other (describe): | | |

Upon funding of this study, flyers will be created.

3. Recruitment Procedures:

- a. Describe how potential subjects will be identified.
- b. Describe how potential subjects are contacted.
- c. Who is recruiting potential subjects?

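### Total SEM AIC cannot compare the social and spatial-social models where the network metrics act as mediators

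*Combined protocol and SAP*

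**What the plan says.** The analysis is introduced in section 12, Statistical Considerations, Aim 2, with this purpose: "To examine the mediating and moderating effects of activity space and social network facilitators and barriers". Step a says that the metrics "will be calculated using a combination of GIS, SNA, and spatial statistics methods", and then gives them a role: "The variables will be the covariates". No units or scaling are given. Step d screens the metrics, so the number carried into each model is not fixed in advance. Step e sets the framework: "Using the framework of structural equation modeling, we will identify the moderating and/or mediating effects".

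The closing paragraph will "contrast the model performance (R², AIC, and RMSE) of two mediation/moderation models" "with the primary (ART adherence) and a secondary (HIV viral suppression) outcome". The two models are "1) with social network metrics and b) with spatial-social network metrics (calculated in step#a").

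The plan does not state which metrics are mediators, moderators or covariates, which likelihood the AIC comes from, whether the two models share a variable set or a set of participants, or which of the three measures decides. On missing answers, section 9 (Risks Associated with Standardized Assessments) says of participants that "they will be able to refuse answering any questions that they do not wish to answer"; the activity space and social network instruments are on that list.

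**The concern.** An AIC difference is meaningful only when both models describe the same variables in the same people. In an SEM a mediator is a modelled variable, so its likelihood is part of the total. If one model has social mediators and the other has spatial-social mediators, the AIC gap contains terms for how many mediators there are, what units they are in, and how well they are themselves predicted. None of these terms measures how well adherence or viral suppression is explained.

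The comparison is there to show whether adding spatial information to network information helps explain the outcomes. AIC is the only one of the three named measures that penalises model size, so it is the natural one to consult on whether extra metrics earn their place. Standard SEM output would supply the total AIC, and that figure can point the wrong way.

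**Working it through.** **Inputs.** n = 90, from the Sample Size and Power Calculations paragraph (3 × 20 + 30 = 90), assuming complete data. The plan states no AIC, R² or RMSE for this comparison, so there is no figure to reproduce. All effect sizes, SDs and units below are assumptions.

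**Formulas.** With X a predictor, M a mediator and Y the outcome:

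- Joint (total SEM) AIC = −2[lnL(M|X) + lnL(Y|X,M)] + 2k
- Outcome-equation AIC = −2 lnL(Y|X,M) + 2k, with k counting only that equation's parameters
- For a Gaussian equation with residual variance s², −2lnL = n[ln(2πs²) + 1]

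Replacing M by cM multiplies the mediator's residual variance by c², which adds n ln(c²) = 2n ln(c) to the joint AIC. In the outcome equation the slope is divided by c and the residuals are unchanged, so nothing is added.

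**Unit shift at n = 90.**

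- c = 2: 180 × ln 2 = 124.8
- c = 10: 180 × ln 10 = 414.5
- c = 1,000 (km to m): 180 × ln 1000 = 1,243.4

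**One simulated data set** (X binary; both metrics 0.3X plus unit-variance noise; Y = 70 + 5X + 2 × social + 10 × spatial, residual SD 15):

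| Model | Joint AIC | Outcome AIC | R² | RMSE |
|---|---|---|---|---|
| Social | 1029.0 | 784.0 | 0.035 | 18.0 |
| Spatial-social, km | 982.0 | 733.0 | 0.453 | 13.6 |
| Spatial-social, m | 2225.4 | 733.0 | 0.453 | 13.6 |

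The joint AIC favours the spatial-social model by 1029.0 − 982.0 = 47.0 in kilometres and the social model by 2225.4 − 1029.0 = 1,196.4 in metres. The other three columns do not move.

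**Repeated samples** (2,000, same set-up). Joint AIC chose the truly better spatial metric in 94.3% of samples at unit scale and in 0% once that metric was doubled. Outcome-equation AIC and R² chose it in 100% of samples on both scales.

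**Two equally predictive metrics** (SD 3 social; SD 2 spatial in km). The expected joint difference, spatial minus social, is 180 × ln(2/3) = −73 in km and −73 + 1,243 = +1,170 in m. Simulation gave −72.6 and +1,170.8, with outcome-equation AIC differing by 0.07.

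**Standardising does not cure it.**

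- Social mediator better predicted by X, spatial mediator better for the outcome, both standardised: joint AIC chose the better outcome model in 0% of samples, outcome-equation AIC in 95.7%.
- One standardised, predictive spatial mediator added to two social ones: joint AIC worsened by 226.3 on average while outcome-equation AIC improved by 32.1. The gap, 226.3 + 32.1 = 258.4, is the cost of the extra mediator equation. As a check, at residual SD 1 that cost is 90 × [ln(2π) + 1] + 2 × 3 = 261.4; it is slightly lower here because X explains a little of the mediator.

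**Moderator only.** With the metric and its product with X conditioned on, outcome AIC was 785.7 (social) against 735.0 (spatial-social), the same in km and m. The problem does not arise.

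**Unequal participants.** Each person missing from one model removes ln(2πs²) + 1 from its outcome −2lnL. For assumed residual SDs of 10, 20 and 30 points this is 7.44, 8.83 and 9.64, so five people missing from one model only would lower its AIC by about 37, 44 or 48. This holds whatever role the metrics have.

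**The case against.** - **Contrast, not ranking.** A reader might infer that the plan ranks the models by AIC. It does not: it contrasts three measures, with no decision rule and no priority for AIC. Outcome R² and RMSE sit beside AIC, do not depend on the metrics' units, and would expose a conflict. This stands, and so does not support a claim that the comparison cannot answer its question at all.
- **The role is left open.** A reader might also infer that the AICs are incomparable in every case. Step a calls the metrics covariates, and the models are described as mediation/moderation. If every metric is conditioned on, both AICs concern the same outcome and are unit-free. This stands as a limit, but mediation is named in the aim, in step e and in the comparison itself.
- **Form of AIC.** A chi-square-based SEM AIC is scale-free for scale-invariant models. That removes the unit effect but not the problem, since it measures fit to two different covariance matrices. In the three-variable model above, which is saturated, chi-square is zero for both and this AIC says nothing about the outcome.
- **Assumed details.** The metric sets are not listed, so their difference is inferred from their labels. Kilometres against metres is a large conversion, and the SDs and effects are invented. The 2n ln(c) shift is algebra and needs no effect size, but it does depend on c and accumulates over every rescaled mediator.
- **Missing answers.** The right to refuse covers all sixteen listed assessments, social network as well as activity space. Nothing shows that spatial answers alone would be missing; unequal samples are a possibility the plan does not exclude.

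**Conclusion.** The concern holds for metrics that act as mediators. There, the usual total SEM AIC describes different variables in the two models and is not a valid basis for comparison. At n = 90 one unit change from km to m moves it by 1,243, and a useful standardised mediator can worsen it (by 226 on average in the case simulated). The unit shift rests on n = 90 with complete data, the −2lnL + 2k form and a Gaussian mediator equation; the simulated figures also rest on assumed effects.

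For metrics entered only as moderators or covariates and conditioned on, AIC is comparable if both models use the same participants. Outcome R² and RMSE are unaffected by the metrics' units, though neither penalises size. The point is worth correcting before analysis because the remedy is nearly free. It concerns a secondary exploratory analysis and does not affect the randomised comparison.

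**What to change.** In the comparative-analysis paragraph after step e of section 12:

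1. State for each metric whether it is a mediator, a moderator or a covariate.
2. Fit both models to the same participants, namely those with both social and spatial metrics.
3. Compare AIC from the outcome equation only: the log-likelihood of adherence, or the logistic log-likelihood of VL<20 copies/mL, given the predictors. Alternatively, fit both SEMs to one common variable set, with the excluded metrics' paths to the outcome fixed at zero. The mediator equations are then the same in both models and cancel. This second route was not simulated here.
4. State that total SEM AIC will not be compared between models with different mediators.

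The cost is a few sentences and a few lines of code. Participants with incomplete metrics are left out of this one comparison. Outcome-equation AIC does not assess the mediator equations; if those matter to the investigators, the common-variable-set route keeps the full SEM.

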2. Risks Associated with Interviews: During the baseline and monthly research interviews, topics such as cocaine use and substance use treatment will be discussed. These topics may make participants feel uncomfortable. Participants may choose not to answer all or any part of a question during the interviews. There are minimal risks expected from participating in the study such as feeling uncomfortable in certain topics being discussed. If anyone feels uncomfortable, they may choose not to answer any part or all of a question. Participant and designated social network member's names will not be used or recorded in the interview data; instead participant study numbers will be used. Yale IRB-approved flyers will be used to help with recruitment for the RCT and the drug treatment counselors will also assist in recruitment of participants. When recruiting participants from venues, participants will be briefly told about the study and if they want to learn more about it, recruiters will hand out a contact information card to call into the study site. No information will be collected from them at this time so they may choose to not to call into the site or if they do call in and want to come in for consenting, information is still not collected and they may decline to come in. Prior to obtaining informed consent, the participant will be read the consent form verbatim and will be asked if they would like to participate in the study or not. They will also be able to decline or take more time to think about it. If they agree, they will be asked to sign the consent form. They may choose to withdraw from the study at any point.

3. Risks Associated with Loss of Confidentiality: As with all research, there is a risk that involves potential breaches of confidentiality. We intend to do everything possible to reduce this risk and this is one of the process measures we propose to measure. All study assessments will be administered in a private setting that will minimize breaches in confidentiality. Patients with substance use disorders, including cocaine, are a vulnerable population. Thus, our research to date has insured strict confidentiality safeguards. We will further increase the protection of these participants by obtaining a Certificate of Confidentiality.

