In addition to the above-mentioned recruitment sources, we will also be able to recruit from the Community Health Care Van (CHCV). The CHCV, a 36-foot van is equipped with two exam rooms, a counseling/phlebotomy room and a waiting area. Partial support from NIDA (R01-DA10186) has enabled the CHCV project to expand service delivery and to reach a number of goals which improve the health care of out-of-treatment drug users. The program currently operates five days (and some evenings) a week in five underserved neighborhoods in New Haven. The CHCV is staffed by a full-time clinical coordinator, a drug treatment coordinator, a case

[figure not shown]
manager, HIV counselors, social workers, mental health workers, clinicians from several hospitals and community health care centers and a dedicated driver/outreach worker. The staff has developed strategic liaisons with patients and providers throughout the community and is capable of connecting researchers with potential HIV-infected patients with co-occurring substance abuse issues.

[figure not shown]
[figure not shown]
[figure not shown]
For the fourth arm, we will be asking the participants to provide us with three names of people in their social network, who has a phone and are willing to send them weekly text reminder to take their medication. Out of the three people, one person will be chosen by the RA to be the social designee. The RA will be contacting all three social designees via phone and upon verbal consent, the social designee will be provided information about the study and their role, and reminded to send text messages to the participants on the weekly basis.

4. Screening Procedures

- a. Will email or telephone correspondence be used to screen potential subjects for eligibility prior to the potential subject coming to the research office? Yes No
- b. If yes, identify below all health information to be collected as part of screening and check off any of the following HIPAA identifiers to be collected and retained by the research team during this screening process.

HEALTH INFORMATION TO BE COLLECTED:

9. **Process of Consent/Assent:** Describe the setting and conditions under which consent/assent will be obtained, including parental permission or surrogate permission and the steps taken to ensure subjects' independent decision-making.

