Aim 2 (Pilot Feasibility Study): Yale IRB-approved fliers will be used to help with recruitment for the RCT and the drug treatment counselors will also assist in recruitment of participants. When recruiting participants from venues, participants will be briefly told about the study and if they want to learn more about it, recruiters will hand out a contact information card to call into the study site. No information will be collected from them at this time so they may choose to not to call into the site or if they do call in and want to come in for consenting, information is still not collected and they may decline to come in. Participants will be provided an informed consent form that will be approved through the Yale University School of Medicine Institutional Review Board (IRB). The participant will be read the consent form verbatim and will be asked if they would like to participate in the study or not. The consent form will outline the agreement to participate in this research study. Participants will indicate consent by signing and dating the informed consent form. All patients will be reminded that their refusal to participate will not negatively affect their relationship with Yale University, local SAT or hospital facilities, their ability to continue in drug treatment, or their ability to obtain medical services from area clinics in the future. They will also be able to decline or take more time to think about it. If they agree, they will be asked to sign the consent form. They may choose to withdraw from the study at any point.

In addition, the following process of consent is going to be followed for the designated social network member for the fourth arm intervention (TRIDENT): a) after randomized to the 4th arm, the RAs and/or the Project Coordinator will ask the participant to call his/her designated social network member, b) the participant will explain the study details from an information sheet to the designee. At this stage the RAs and/or the Project Coordinator will also help in explaining the role

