of the designee in the intervention, c) We will obtain a verbal consent from the designees as minimal risk is involved. The risk is minimal for designees because: a) the designees are not answering any questions, b) they are not completing any surveys at the study sites, c) they will use their own phone to send text messages to the participant, d) the data from the messages will be downloaded from the patient's phone and not from the designee's phone, and e) after obtaining the verbal consent, the designee will be given a unique ID and their name or phone number will not be used.

10. Evaluation of Subject(s) Capacity to Provide Informed Consent/Assent: Indicate how the personnel obtaining consent will assess the potential subject's ability and capacity to consent to the research being proposed.

The study interviewers are trained in interviewing and will assess the subject's understanding through verbal responses and non-verbal cues. Interviewers will ask open ended questions while introducing the details of the study to the subject such as "Can you tell me what you understood from our discussion?" or "What should you do if you want to stop participating in this study?" and will use IRB approved consent forms during informed consent procedure. If the interviewer determines that the subject does not fully comprehend the study purpose and his or her role as a participant, the subject will not be consented and will not be eligible for the study.

11. Documentation of Consent/Assent: Specify the documents that will be used during the consent/assent process. Copies of all documents should be appended to the protocol, in the same format that they will be given to subjects.

Aim 1 (Focus Groups): No signed consent forms will be required for the focus group participants since signatures would be the only identifiers. An IRB-approved consent form will be read verbatim and assent will be given verbally. Additionally, a copy of the consent form will be given to the participants.

Aim 2 (Pilot Feasibility Study): A compound consent and authorization form will be used (attached in this application).

No signed consent forms will be required for the designated social network members, involved in the 4th arm of Aim 2, since their health and personal identifiers are not used in the study. An IRB-approved information sheet will be read verbatim and assent will be given verbally. A unique ID will be provided for the designee and their names will not be used.

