12. Non-English Speaking Subjects: Explain provisions in place to ensure comprehension for research involving non-English speaking subjects. If enrollment of these subjects is anticipated, translated copies of all consent materials must be submitted for approval prior to use.

All consent forms, information sheets and study documents will be available in English and Spanish. Our team consists of individuals who are bi-lingual/bi-cultural in Spanish and English.

[figure not shown]
12(a) As a limited alternative to the above requirement, will you use the short form* for consenting process if you unexpectedly encounter a non-English speaking individual interested in study participation and the translation of the long form is not possible prior to intended enrollment?

YES NO

Note* If more than 2 study participants are enrolled using a short form translated into the same language, then the full consent form should be translated into that language for use the next time a subject speaking that language is to be enrolled.

Several translated short form templates are found on our website at: <http://www.yale.edu/hrpp/forms-templates/biomedical.html>. If the translation of the short form is not available on our website, then the translated short form needs to be submitted to the IRB office for approval via amendment prior to enrolling the subject. *Please review the guidance and presentation on use of the short form available on the HRPP website.*

If using a short form without a translated HIPAA Research Authorization Form, please request a HIPAA waiver in the section above.

SECTION VIII: PROTECTION OF RESEARCH SUBJECTS

Confidentiality & Security of Data:

- a. What protected health information (medical information along with the HIPAA identifiers) about subjects will be collected and used for the research?

Private identifiable data about study participants including their names, age, sex, ethnicity, addresses, phone numbers and other contact information, photos, dates of birth will be collected. Names and phone numbers will be collected from social designee for the fourth arm. All confidential information (study instruments etc.) will be recorded with study participant number only, maintained in locked cabinets within our offices at the Yale University AIDS Program and will only be available to be opened by the Data Manager, Project Manager or the Principal Investigator.

- b. How will the research data be collected, recorded and stored?

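### The plan describes two conflicting ways of enlisting the Group D social contact, and its grounds for verbal consent conflict with how that contact's name and number are used

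*Combined protocol and SAP*

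**What the plan says.** Section VII item 3 (Recruitment Procedures) says of the fourth arm that "we will be asking the participants to provide us with three names of people in their social network", each of them someone "who has a phone and are willing to send them weekly text reminder to take their medication". It continues: "Out of the three people, one person will be chosen by the RA to be the social designee". The next sentence reads: "The RA will be contacting all three social designees via phone and upon verbal consent, the social designee will be provided information".

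Section VII item 9 (Process of Consent/Assent) sets out a different sequence for the same step. After randomization to the fourth arm, staff "will ask the participant to call his/her designated social network member". The participant explains the study from an information sheet with staff help, and verbal consent follows. One of the five grounds given there for minimal risk is that "the designee will be given a unique ID and their name or phone number will not be used". Section VII item 11 (Documentation of Consent/Assent) then drops the signature because designees' health and personal identifiers are not used.

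Section VIII item a states: "Names and phone numbers will be collected from social designee for the fourth arm". The intervention text (Research Plan, 2.E) sends a weekly prompt to the designee's phone. Minimizing Risks (item 10) deletes downloaded messages whose sending number does not belong to a consented designee.

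Risks (item 9), under loss of confidentiality, says that "there is a risk that involves potential breaches of confidentiality. We intend to do everything possible to reduce this risk".

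**The concern.** Staff cannot follow both enlistment procedures. The recruitment text is also inconsistent within itself: it selects one designee and then has three designees phoned.

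The difference affects confidentiality. A call from a research office to someone whom a participant named, about weekly medication reminders, can link that participant to a study about medication. The plan guards against such links elsewhere, with staggered appointments, a choice of exits and offices shared by many studies. It sets no limit on what a nominee who is not chosen may be told, and its risk list does not mention disclosure to nominees or designees.

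The second matter is the basis for verbal consent. If one stated ground does not match the procedures, the ethics board is relying on a description that the plan does not bear out.

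**Working it through.** The plan gives no figure of its own here, so the check is a comparison of texts and a count.

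**Enlisting the designee**

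| Point | Section VII item 3 | Section VII items 9 and 11 |
|---|---|---|
| Who calls | RA | Participant, with staff helping |
| How many are called | Three | One |
| Who receives study information | The designee (singular) | The designee |
| Order | Information after verbal consent | Explanation, then verbal consent |

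The intervention text prompts one designated member per participant. No section gives a reason for phoning the other two.

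**Count of people phoned**

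Inputs: 3 nominees and 1 designee per participant (Section VII item 3); Group D = 30 (Sample Size and Power Calculations); total 90, allocated 1:1:1:1 (2.D Randomization). The last two sources disagree on the size of Group D, so both are used.

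- Group D = 30: phoned 3 × 30 = 90; not designees (3 − 1) × 30 = 60.
- 1:1:1:1: 90 / 4 = 22.5, so 22 or 23 participants; phoned 3 × 22 = 66 to 3 × 23 = 69; not designees 2 × 22 = 44 to 2 × 23 = 46.
- Under the consent section: 30 people (or 22 to 23), plus replacements for refusals.

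These count people phoned. The 60, or 44 to 46, is therefore an upper bound on the people without a role who learn of a participant's involvement. (The 90 people phoned equals the trial's total enrolment only by coincidence.)

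**Use of the designee's identifiers**

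- Stated: name or phone number not used (Section VII item 9); personal identifiers not used (Section VII item 11).
- Name and number collected: Section VIII item a.
- Number used for weekly prompts: Research Plan, 2.E.
- Number used to filter messages: Minimizing Risks.

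The two statements of non-use cannot stand without a qualification that neither contains. Section VIII item a also mentions only the designee, whereas the recruitment text requires names and working numbers for all three nominees.

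**The case against.** A reader might infer that the recruitment text has two unneeded people per participant told about an HIV and cocaine study. The documents do not support that. They give study information only to the designee, in the singular, and only once verbal consent is given. No section says that the other two are told anything, and none says that the call mentions HIV or cocaine. The only example content is a generic reminder to take medication. Nor is it shown that the calls are pointless: they might check willingness or secure a backup, and the participant nominated all three for this role. What stands is that no purpose and no limit are written down.

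On order, the recruitment sentence is a brief summary, and its verbal consent could mean agreement to hear more. The consent section is the fuller text. This makes the conflict on order the weakest of the three, but the wording still needs correcting.

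On identifiers, the non-use clause is one of five grounds and the other four are not in question. Elsewhere the plan limits the same idea to interview data and labels study materials by number. The clause may well concern data labelling rather than operational contact. It would go too far to call it simply false or to say that the minimal-risk judgement collapses. The clause does not state that scope, however, and the signature waiver repeats it unqualified.

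Finally, consent pages are absent from the review copy and the designee information sheet is not shown. Participants may already be warned about contact with nominees.

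**Conclusion.** The plan contradicts itself on who enlists the Group D designee and how many people are phoned and, on a literal reading, on whether information precedes verbal consent. The recruitment text creates a foreseeable but unstated risk of revealing a participant's involvement to up to two people with no stated role. The bound is 60 people with Group D at 30, or 44 to 46 under equal allocation, assuming full enrolment, three nominees per participant and every nominee phoned. Actual disclosures could be far fewer, including none.

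Separately, the stated non-use of designee identifiers conflicts with three other sections unless it is limited to the study data. No effect on outcomes, sample size or analysis is claimed. The changes should be made because they are cheap and serve the plan's own confidentiality commitment.

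**What to change.** 1. Reconcile Section VII item 3 with items 9 and 11 so that only the chosen nominee is contacted, and a second nominee only if the first declines. State who makes the call.
2. Put information before verbal consent in both places.
3. State what any contacted nominee, including one who declines, may be told about the participant and the study.
4. Add disclosure to nominees and designees to the Risks section, and to the participant consent form if it is not already there.
5. Reword the identifier statements in Section VII items 9 and 11 to say that the designee's name and number are held for prompting and message filtering, apart from the study data. Make Section VIII item a cover nominees as well.

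The cost is protocol and information-sheet wording and an IRB amendment, with fewer calls for staff. There are two downsides. Enlistment is delayed briefly when the first nominee declines. If the participant makes the call, a friend or relative may feel pressed to agree, so staff should confirm that agreement is free.
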